4 EOT visit should take place 6 (up to 10) weeks after last treatment. If treatment is discontinued due to progressive disease (PD), initiation of new anti-NB treatment prohibited as per protocol, withdrawal from the trial or investigator judges it warranted due to medical reasons/non-compliance, the patient should be called for EOT visit as soon as possible and subsequently be followed for safety and new anti-cancer therapy for 6 weeks after last treatment, and herafter continue in the long-term follow-up.

5 Long-term follow-up (FU) evaluations should take place approximately every 4 months until 2 years after End of Treatment. During long-term FU, information on death, PD, serious adverse events (SAEs) ongoing at EOT, new SAEs at least possibly related to naxitamab, new onset of secondary malignancies and autoimmune diseases should be collected. Furthermore, new anti-cancer therapy should be collected as concomitant medication. (see Section 9.1).

6 Screening imaging and BM examination must be obtained at least 10 calendar days after any prior anti-cancer treatment.

7 Only applicable for D-3 to 0 in cycle 1.

8 Height, weight, physical examination, clinical laboratory assessments, anti-drug antibodies (ADA) and performance test must be performed prior to dosing in each cycle; prior to day (D)1 or at D1.

9 Serum pregnancy test must be done on D-3 prior to gabapentin administration for women of childbearing potential

10 Should only be performed at D15 during C1.

11 Bilateral aspirates and bone marrow (BM) biopsies (2+2), performed at screening and after C2, C4, C8, C13, and EOT. In addition, for patients who achieve a first CR or PR after C4 or a first CR or PR after C8 a confirmatory response assessment should be performed within 4-6 weeks after detection of the overall response. Samples for RTqPCR should be taken at Screening and after C2 and C4. See section section 9.1.2

12 Imaging schedule follows timing of BM biopsies (see #11 above). For a Fluorodeoxyglucose Positron Emission Tomography/ Computed Tomography (FDG PET/CT) scan, the patient must be in fasting state for at least 4 hours prior to the scan. If the patient is not fasting serum glucose determination must be performed prior to the administration of FDG. Please refer to the imaging acquisition guideline for more details.

13 Not to be performed at EOT if the patient discontinue treatment due to PD, provided that PD is documented by scan and/or biopsy. See section [section 9.1.2](#)

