4.2 Rationale for antibody therapy for High-Risk NB

The disialoganglioside GD2 is an adhesion molecule abundantly expressed in NB¹⁰. This genetically stable antigen is rarely lost and relatively inert on the cell membrane. Monoclonal antibodies (mAbs) that target GD2 have shown clinical efficacy in the treatment of GD2 expressing tumors. This includes metastatic cancer in well-vascularized sites of metastases, such as BM infiltrated by NB cells^{10,11}. Three anti-GD2 mAbs are currently approved for the treatment of high-risk NB. Dinutuximab (Unituxin[®]) and naxitamab (Danyelza[®]) are approved in the United States (US) for the treatment in the post-consolidation setting and of relapsed/refractory NB in the bone and/or BM, respectively^{12,13}. Dinutuximab beta (Qarziba[®]) is approved in the European Union (EU) for the treatment in the post-consolidation setting and of relapsed or refractory NB¹⁴. Dinutuximab and dinutuximab beta contain significant murine fractions and represent so called chimeric antibodies. Rapid production of human anti-chimeric antibody (HACA) can develop in patients and can delay treatment, prevent further cycles, and compromise anti-tumor effects of the mAb treatment. Furthermore, treatment with these antibodies requires long time infusions; dinutuximab is administered over 10

to 20 hours for 4 consecutive days; dinutuximab beta is administered over 8-hours for 5 days or during continuous infusion with a pump for 10 days. Treatments are typically performed or initiated in the in-patient setting. Humanization of the anti-GD2 antibody reduces or eliminates the mouse epitopes and has the potential to reduce development of such anti-drug-antibody (ADA) responses. Furthermore, a shorter infusion time may decrease the treatment burden for patients and their families. Naxitamab represent such an approach.

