6.2 Secondary Endpoints

1. ORR after 2 cycles defined as the proportion of patients obtaining a centrally assessed CR or PR according to the INRC at completion of two treatment cycles
2. Duration of response (DoR), defined as the time from first centrally assessed OR (CR or PR according to the INRC) to PD or death
3. CR rate, defined as the proportion of patients obtaining a centrally assessed CR according to the INRC at or before completion of four treatment cycles
4. CR rate after two cycles defined as the proportion of patients obtaining a centrally assessed CR according to the INRC at completion of two treatment cycles
5. Minor response (MR) rate, defined as the proportion of patients obtaining a centrally assessed MR according to the INRC at or before completion of four treatment cycles
6. "MR or better" rate, defined as the proportion of patients obtaining a centrally assessed CR, PR or MR according to the INRC at or before completion of four treatment cycles
7. Proportion of patients with disease in BM at enrollment who obtain centrally assessed CR in BM and convert to minimal residual disease (MRD) negative (assessed by reverse transcriptase-quantitative polymerase chain reaction (RTqPCR)) at or before completion of four cycles
8. Time to First Subsequent Therapy or death (defined as the time from initiation of treatment with investigational medicinal products (IMP) until death or start of new anti-cancer treatment (prohibited as per protocol))
9. PFS defined as the time from first IMP administration until centrally assessed PD or death, whichever comes first
10. OS defined as the time from first IMP administration until death
11. 1- and 2-years PFS defined as the proportion of patients alive and with no centrally assessed PD at 1- and 2 year, respectively after first IMP administration
12. 1- and 2-year OS defined as the proportion of patients alive at 1- and 2 years after first IMP administration
13. Safety incl. incidence of AEs and SAEs graded according to Common Terminology Criteria for AEs (CTCAE) version 5.0
14. Pain during naxitamab infusions as assessed by Wong Baker- and FLACC scales
15. Incidence of ADA (including assessment for neutralizing potential and time to first positive ADA assessment from first day of naxitamab administration)
16. Number of naxitamab infusions done in an out-patient setting defined as infusions not requiring admission to hospital due to adverse events

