7.11.2 Exclusion Criteria

1. A diagnosis of myelodysplastic syndrome or any malignancy other than NB
2. Any systemic anti-cancer therapy, including chemotherapy, or immunotherapy, within 3 weeks prior to enrollment
3. ASCT within 6 weeks prior to enrollment or ongoing toxicity due to the stem cell transplant at the discretion of the investigator
4. Therapeutic ¹³¹I-MIBG within 6 weeks prior to enrollment
5. RT within 4 weeks prior to enrollment at the site of any lesion that will be identified as a target lesion to measure tumor response. Lesions that have been previously radiated cannot be used as target lesions unless there is radiographic evidence of progression at the site following radiation or a biopsy done following radiation shows viable NB. There are no time restrictions following prior RT for non-target lesions or for palliative radiation to sites that will not be used for response assessment
6. Prior treatment with anti-GD2 therapy if the patient experienced PD while on anti-GD2 treatment
7. Receipt of second line chemotherapy after designation of primary refractory disease or first relapse or PD
8. Patients with NB in BM only
9. NB in the CNS or leptomeningeal disease within 6 months prior to enrollment
10. Performance status of < 50% as per the Lansky scale (patients less than 16 years of age) or Karnofsky scale (for patients aged 16 years or older)
11. Life expectancy of less than 6 months, as judged by the Investigator
12. Left ventricular ejection fraction < 50% by echocardiography
13. Inadequate pulmonary function defined as evidence of dyspnea at rest, exercise intolerance, and/or chronic oxygen requirement. In addition, room air pulse oximetry < 94% and/or abnormal pulmonary function tests if these assessments are clinically indicated
14. Patients with \geq Grade 2 diarrhea
15. Treatment with long-acting myeloid growth factor within 14 days or short-acting myeloid growth factor within 7 days prior to first dose of GM-CSF
16. Treatment with immunosuppressive treatment (local steroids excluded) within 4 weeks prior to enrollment
17. Life threatening infection(s)
18. Patients with uncontrolled seizure disorders despite anticonvulsant therapy (defined as a seizure event within 3 months prior to enrollment)
19. Treatment with enzyme-inducing anticonvulsants including phenytoin, phenobarbital, or carbamazepine for at least 7 days prior to enrollment
20. Concomitant use with St John's wort

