8.1.2.3 Naxitamab

On days when co-administered with GM-CSF, naxitamab infusion is started ≥ 60 min after GM-CSF.

On days when co-administered with IT (i.e., Days 2 and 4), it is recommended to start naxitamab infusion at least 1 hour after irinotecan administration to allow for preparations and administration of pre-medications.

Naxitamab should be infused IV at 2.25 mg/kg/day on Days 2, 4, 8 and 10 for a total dose of 9 mg/kg per cycle (Please refer to Appendix 2 for details on naxitamab treatment if the patient has discontinued IT treatment due to toxicity). Administration of naxitamab should be adjusted according to Section 8.4.5, if selected naxitamab adverse reactions are observed. If any events occur fulfilling a general discontinuation criterion the patient must be withdrawn from all treatments immediately and enter long-term FU, see Section 7.12.

At Cycle 1 Day 2 (C1D2):

Naxitamab should be infused over approximately 60 min.

All subsequent naxitamab infusions:

Naxitamab should be infused over approximately 30 min.

Special circumstances

The infusion may be given over approximately 60 min. at Day 2 of any cycle at the investigator's discretion if:

- The patient during C1D2 experienced naxitamab related hypotension:
 - Grade 4 **or**
 - Grade 3 not adequately responding to intervention
- At the investigator's discretion due to severe infusion related adverse drug reactions not adequately responding to interventions

The 60/30 min infusion time is a minimum infusion time. If infusion pause or infusion rate reduction is required due to infusion related AE (see Section [8.4.5](#)) the infusion time will become longer.

Naxitamab treatment in an out-patient setting is defined as a naxitamab infusion performed in the ambulatory setting.

In-patient treatment (i.e. requiring hospitalization) includes both short term admissions and admissions requiring overnight stay.

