11.2 Immunogenicity

Samples for assessment of anti-drug antibodies (ADA) should be sent to a special laboratory for analysis. Please refer to the laboratory manual for more information.

Table 10 ADA samples

ADA assessment: Prior to dosing in each cycle EOT	
• Anti-naxitamab antibodies*
---	--

*Analyses will be performed in batches. Therefore, results will not be available during the trial

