12.11 Subgroup Analyses

The primary endpoint will be analyzed and presented for the following subgroups:

- primary refractory vs. first relapse vs first PD during frontline therapy
- soft tissue lesions present at baseline (yes / no)
- tumor MYCN amplification status (yes / no)
- prior exposure to anti-GD2 antibody therapy (yes / no)
- ADA status (negative at all times / positive at any time)
- disease compartment (bone, BM, bone and BM combined (*i.e.*, OR excl. soft tissue lesions) as well soft tissue)
- geographical region

- site
- age group (0 - <2, 2 - <6, 6 - <12, 12 - <18 and >=18 years)
- body weight group (<20 kg; 20-<50 kg; >=50 kg)
- sex (male/female)
- race

Overviews of AEs will be presented for the following subgroups:

- primary refractory vs. first relapse vs first PD during frontline therapy
- ADA status (negative at all times / positive at any time)
- geographical region
- age group (0 - <2, 2 - <6, 6 - <12, 12 - <18 and >=18 years)
- body weight group (<20 kg; 20-<50 kg; >=50 kg)
- sex (male/female)
- race

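### The ADA subgroup and the ADA incidence endpoint do not separate patients already positive before the first naxitamab dose from those who become positive on treatment

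*Combined protocol and SAP*

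**What the plan says.** Section 12.11 lists a subgroup, "ADA status (negative at all times / positive at any time", for both the primary endpoint and the AE overviews. Secondary endpoint 15 in Section 6.2 is "Incidence of ADA (including assessment for neutralizing potential and time to first positive ADA assessment from first day of naxitamab administration". Section 12.7 plans ADA summary tables and listings. It also plans a figure of time to first positive result, restricted to patients in whom ADA arise in the course of the trial; the restriction is not defined further.

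On sampling, Table 10 in Section 11.2 has ADA taken "Prior to dosing in each cycle" and at end of treatment. A flow chart footnote in Section 3 fixes the timing: "anti-drug antibodies (ADA) and performance test must be performed prior to dosing in each cycle; prior to day (D)1 or at D1". On dosing, Section 8.1.2.3 says "Naxitamab should be infused IV at 2.25 mg/kg/day on Days 2, 4, 8 and 10".

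On prior exposure, exclusion criterion 6 in Section 7.11.2 bars "Prior treatment with anti-GD2 therapy if the patient experienced PD while on anti-GD2 treatment", and criterion 24 bars a history of Grade 4 anaphylaxis on such therapy. Anti-GD2 exposure is otherwise allowed, no criterion concerns existing ADA, and Section 12.11 has a further subgroup, "prior exposure to anti-GD2 antibody therapy (yes / no".

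**The concern.** The subgroup rule looks at every sample equally, including the one that cannot reflect the trial's naxitamab. A patient who enters with reactivity in the assay and never develops more is classed as ADA positive for response and for adverse events. The row then mixes two kinds of patient: those who came in positive, perhaps because of earlier treatment, and those who became positive on naxitamab. Because the route to baseline positivity is likely to run through prior anti-GD2 therapy, the row may in part restate the prior-exposure subgroup.

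The incidence endpoint has the same gap. It does not require a negative pre-dose sample, so a tabulation of every patient with a positive result would satisfy its wording. The plan does draw this distinction for adverse events: Sections 12.5 and 12.5.1 separate pre-treatment from treatment-emergent events. It draws none for ADA.

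ADA-positive groups are small. Section 4.3.2 reports only two such patients in Trial 201 at its interim analysis and calls the information on them very limited. A few baseline-positive patients could therefore make up much of the row.

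**Working it through.** The plan states no figure for baseline ADA positivity, so there is none to reproduce. The check has two parts.

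**Timing.** Table 1 places the first ADA sample in the window from Day -3 to Day 0 or on Day 1. The first naxitamab infusion is on Day 2.
- Latest sample: 1 - 2 = -1 day.
- Earliest sample: -3 - 2 = -5 days.

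So the cycle 1 sample always precedes naxitamab. If a baseline-positive patient were given a time to first positive, counted from the first naxitamab day as endpoint 15 specifies, it would be -5 to -1 days.

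**Size under assumptions.** From the documents:
- N = 52 dosed patients (Section 12.2).
- ADA rates of 8.3% (Trial 201) and 23.1% (Trial 12-230) from Section 4.3.2, used here as alternative on-treatment rates r.

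Assumed, because the documents give neither:
- the share with prior anti-GD2 exposure, e = 30% to 70%;
- the share of the exposed who are positive before dosing, b = 5% to 20%;
- no baseline positivity in unexposed patients, and r applying to everyone negative at baseline.

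Baseline positives: B = 52 × e × b. Any-time positives: A = B + r × (52 - B). Share of the positive row that was positive at baseline: B / A.

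| e, b | B | r | A | A / 52 | B / A |
|---|---|---|---|---|---|
| 30%, 5% | 0.78 | 8.3% | 0.78 + 0.083 × 51.22 = 5.0 | 9.7% | 16% |
| 50%, 10% | 2.60 | 8.3% | 2.60 + 0.083 × 49.40 = 6.7 | 12.9% | 39% |
| 70%, 20% | 7.28 | 8.3% | 7.28 + 0.083 × 44.72 = 11.0 | 21.1% | 66% |
| 30%, 5% | 0.78 | 23.1% | 0.78 + 0.231 × 51.22 = 12.6 | 24.3% | 6% |
| 50%, 10% | 2.60 | 23.1% | 2.60 + 0.231 × 49.40 = 14.0 | 26.9% | 19% |
| 70%, 20% | 7.28 | 23.1% | 7.28 + 0.231 × 44.72 = 17.6 | 33.9% | 41% |

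The effect depends strongly on the on-treatment rate. At 8.3% the any-time rate is 1.2 to 2.5 times the on-treatment rate (9.7 / 8.3 and 21.1 / 8.3). At 23.1% it is 1.1 to 1.5 times (24.3 / 23.1 and 33.9 / 23.1).

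**The case against.** A reader might infer that antibodies carried over from earlier therapy are counted as ADA arising in this trial, and that naxitamab's immunogenicity is therefore overstated against the earlier trials. The documents do not support that, for four reasons.

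- **No text says so.** Section 12.11 only labels a subgroup. Section 12.7 is about ADA formation and limits its figure to patients who develop ADA while on trial; incidence ordinarily means new cases. On that reading a baseline-positive patient is left out of the figure, and the negative times never appear.
- **Carry-over is not shown.** Section 4.2 says of the chimeric products that "Rapid production of human anti-chimeric antibody (HACA) can develop in patients", but the assay in Table 10 is for anti-naxitamab antibodies. Nothing says that antibodies to other anti-GD2 products react in it. Prior naxitamab is not excluded, but no frequency is given.
- **Comparability is unknown.** Section 4.3.2 does not say how baseline positives were handled in Trials 12-230 and 201.
- **Detail is deferred.** Section 12.13 leaves further description to the SAP, and an ever-positive versus never-positive split is usable in its own right, since pre-existing antibody could also affect response or tolerability.

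These points remove the stronger inference. They do not remove the gap. The wording in Section 12.7 covers one figure and is repeated neither in endpoint 15 nor in Section 12.11. The any-time rule is stated explicitly, and the deferral in Section 12.13 does not mention ADA. No ADA rule beyond these sections appears in the text supplied. The gap also does not depend on cross-reactivity: any positive pre-dose result, whatever its source, has the same effect.

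**Conclusion.** The point holds as a gap in definition. Section 12.11, read as written, puts baseline-positive patients in the ADA-positive row for ORR and AEs; endpoint 15 does not exclude them from incidence; and Section 12.7 implies a different definition for one display. How many patients this touches cannot be computed from the documents. Under the assumed ranges it is about 1 to 7 of 52, with an any-time rate of about 10-21% or 24-34% depending on which cited ADA rate applies on treatment. The consequence is confined to a secondary endpoint, which the synopsis does not list as key, and to descriptive subgroups. The primary test, N and power do not change.

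**What to change.** Use one set of definitions in Sections 6.2, 12.7 and 12.11, or in the SAP:

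- **Treatment-induced ADA:** negative before the first naxitamab dose and positive on a later sample. State how a missing pre-dose sample is handled.
- **Treatment-boosted ADA:** positive before the first dose with a titre rise afterwards, if titres are measured; the documents do not say whether they are. Without this category, a baseline-positive patient whose antibodies rise on naxitamab would never count.
- **Treatment-emergent ADA:** the two together.

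Report incidence and time to first positive for treatment-induced ADA. Report pre-dose prevalence separately, overall and by prior anti-GD2 exposure. In Section 12.11, show baseline-positive patients apart from treatment-emergent and never-positive patients, stating where treatment-boosted patients are placed. Keep the any-time split as supplementary, because the cells will be small.

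This is a free improvement: wording and re-tabulation only. The pre-dose sample is already scheduled, and no visit or assay is added. Section 11.2 says ADA samples are analysed in batches with no results available during the trial, so the definitions can be fixed before any result is seen.

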12.12 Handling of Missing Data

Handling of patients not evaluable for the efficacy endpoints is described in Section [12.4.1](#). Handling of AEs with unknown onset dates is described in Section [12.5](#) and handling of AEs with onset outside reporting periods is described in Section [12.5.1](#).

12.13 Statistical Analysis Plan

The Statistical Analysis Plan (SAP) will in further detail describe the analyses presented above.

Handling and presentation of data such as prior cancer therapies, demographics, baseline disease status, trial drug exposure, other trial assessments and protocol deviations (incl. COVID-related ones) will be described in the SAP. In addition, analyses of the proportion of patients who discontinue IT due to unacceptable toxicity and subsequently receive naxitamab + GM-CSF alone, and the time to such a discontinuation, will be described in the SAP.

12.14 Reporting of trial results

The results from this trial will be presented in a Clinical Study Report (CSR).

13 ETHICS

13.1 Independent Ethics Committee (IEC) or Institutional Review Board (IRB)

This protocol and any accompanying material to be provided to the patient (such as patient information sheets and/or descriptions of the trial used to obtain informed consent) will be submitted by the Investigator to an IRB/IEC. Approval from the IRB/IEC must be obtained before starting the trial and should be documented in a letter to the Investigator.

It is the responsibility of the Investigator or his/her representative to obtain approval from the IRB/IEC before enrolment of any patient into the trial for the trial protocol/protocol amendments, advertisements, the patient information and the Informed Consent, including any written material to be given to the patient.

13.2 Ethical Conduct of the Trial

The trial will be conducted in accordance with the protocol, applicable regulatory requirements, ICH Good Clinical Practice⁴⁵ (GCP and the ethical principles of the Declaration of Helsinki⁴⁶ as adopted by the 18th World Medical Assembly in Helsinki, Finland, in 1964 and sub-sequent versions.

The trial will be conducted according to Ethical Considerations for Clinical Trials on Medicinal Products Conducted with the Pediatric Population⁴⁷ (recommendations of the ad hoc group for the development of implementing guidelines for Directive 2001/20/EC relating to GCP in the conduct of clinical trials on medicinal products for human use).

13.3 Patient Information and Informed Consent

The Investigator or his/her designee must obtain the written informed consent from each patient, and/or the patients acceptable authorized representative, before any trial related procedures are performed as applicable to local regulations. The written patient information must not be changed without prior discussion with the Sponsor and approval by the IRB/IEC. Patient and legal representative (e.g., parent(s) or guardian(s)) must receive full trial information, both verbally and written, before consent is given. A child or adolescent patient will be informed and included in the conversations with the parents, to the extent that he/she can understand given his/her age. A patient information sheet will be prepared addressing legal representative(s) and a version especially addressing the adolescent population will also be prepared, if applicable according to local regulations.

The patient information will contain full and adequate verbal and written information regarding the objective and procedures of the trial and the possible benefits and risks involved. This will include any information of possible transfer of biological materials, imaging and other needed for central analysis. Regardless of legal representative(s) written consent, the participation shall not take place if the patient objects. Objection can also be non-verbal and expressed by the child's attitude, body language or resistance. Informed Consent (parents), and if applicable informed assent (child/adolescent), must be signed in accordance with local regulations.

If applicable to local regulations: if the child turns 18 during his/her participation in the trial, a written consent must be obtained from him/her before the trial can continue.

Before signing the ICF, the patient/parents must be given sufficient time to consider the possible participation. Further, each patient must be informed about their right to with-draw from the trial at any time. Parents and patients will also be informed that research participation is voluntary but if they withdraw from the trial, their data will still be used. When the informed consent form has been signed, the patient/parent(s) receives a copy of the signed form and the original is retained in the Investigator site file. A second copy may be kept in the patient's medical notes. The informed consent forms must be signed and dated both by the signee and by the person providing the information to the patient/parents. It is recommended to notify the patient's family doctor of the patient's consent to participate in the trial.

